PASS Information

Title	Utilisation of dulaglutide in European countries: A cross-sectional, multi-country and multi-source drug utilisation study using electronic health record databases.
Version identifier	Version 1.0
Date of last version	01 May 2016
EU PAS Register No:	Study not registered
Active substance	Dulaglutide (ATC code: A10BX)
Medicinal product(s):	Trulicity 0.75 mg solution for injection Trulicity 1.5 mg solution for injection
Product reference:	EU/1/14/956
Procedure number:	EMA/H/C/002825
Marketing authorisation holder(s)	Eli Lilly Nederland B.V.
Joint PASS	No
Research question and objectives	
The purpose of this study is to describe how dulaglutide is used among different patient groups in European countries.
 
Primary objective: To describe the frequency of dulaglutide use in the population and characterise by age, gender, main co-morbidities and main co-prescriptions overall and in the following subgroups of interest:
 
 ○ Populations of interest: 
 • Patients with severe renal failure • Patients with hepatic disease • Patients with heart failure • Patients with severe gastrointestinal disease • Children and adolescents <18 years of age • Elderly patients ≥75 years • Pregnant and breastfeeding women ○ Medication use : 
 • Medication errors • Off-label use 
Secondary objective: To describe the off-label use among each of the above populations of interest.

Country(-ies) of study	Several countries will be selected from the databases under consideration (France, Germany, Spain, Sweden and the United-Kingdom) based on the criteria described in the feasibility analysis (see Section 9.5.2).
Author	IMS Health [name], Medical director [name], Senior Medical writer and project lead

Approval Date: 07-Jun-2016 GMT

Marketing Authorisation Holder

Marketing authorisation holder (MAH)	Eli Lilly Nederland B.V.
MAH contact person	[name], Pharmacoepidemiologist Eli Lilly and Company

1. Table of Contents

Section	Page
1. Table of Contents.....	3
2. List of Abbreviations	7
3. Responsible Parties	9
4. Abstract	10
5. Amendments and Updates.....	14
6. Milestones.....	15
7. Rationale and Background	16
8. Research Question and Objectives.....	17
9. Research Methods.....	18
9.1. Study Design.....	18
9.2. Setting and Population.....	18
9.2.1. Setting.....	18
9.2.2. Inclusion Criteria	18
9.2.3. Population of Interest	18

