9.2.2. Inclusion Criteria

The eligible patients are those who meet the following criteria:

- Patients for whom a treatment with dulaglutide is initiated during the observation period.
- Patients having at least 6 months of available continuous history prior to the date of the first dulaglutide prescription.

No exclusion criteria will be applied to the study.

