9.3. Variables

Regardless of the coding system used in the database, different populations and subgroups of interest are defined as follows:

Treatment initiation with dulaglutide:

- any record of prescription of dulaglutide during the observation period without prior record of prescription of the same product in the available patient's history
- if no prior history is available to check the above criteria, the prescription is not considered as an initiation

Patients presenting with T2DM:

- with any recorded diagnosis code for T2DM
- or with any recorded treatment code for an ADM other than insulin
- or, with any recorded treatment code for insulin initiated at age >30 (defined as no record of insulin therapy during 6 months prior to first record of insulin treatment)
- or with any record of unspecified diabetes mellitus diagnosis at age >30 and without history of insulin therapy (defined as no record of insulin therapy during 6 months prior to first record of diabetes diagnosis),
- a sensitivity analysis will be conducted to determine the age threshold mentioned above (see section 9.7.3 Sensitivity analysis).

Patients with severe renal failure:

- with a recorded diagnosis of severe renal failure
- or with a recorded glomerular filtration rate (eGFR) value <30 ml/min/1.73 m²

Patients with hepatic disease:

- with a recorded diagnosis of any hepatic disorder

Patients with heart failure:

- with a recorded diagnosis of heart failure

Patients with severe gastrointestinal disease:

- with a recorded diagnosis of any of the following conditions:
 - cancer of the gastrointestinal tract,
 - diseases of the oesophagus,
 - active ulcer at the time of drug initiation (gastric, duodenal, gastro-jejunal, peptic ulcer of unspecified site),
 - active haemorrhagic gastritis, chronic atrophic gastritis, adult hypertrophic pyloric stenosis, obstruction of duodenum, and other motility disorders,
 - digestive fistula,
 - Crohn's disease, ulcerative colitis,
 - diverticular disease of the intestine,
 - severe vomiting, severe diarrhoea and severe constipation
 - motility disorders, including ileus, gastroparesis, et cetera,
 - infectious and inflammatory situations (appendicitis, cholecystitis, cholangitis).

Children and adolescents:

- Age < 18 at the time of treatment initiation
(subgroups of analysis: 0-4, 5-9, 10-14, and 15-17 years old).

Elderly:

- Age \geq 75 at the time of treatment initiation.

Pregnant and breastfeeding women:

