- Any record of pregnancy or breast feeding at the time of treatment initiation.

Patients with medication errors:

- Prescribed and/or administered > 1 dose per week of dulaglutide (6).
- The number of doses/week will be calculated by measuring the time span between the current prescription and the next one (in weeks) and dividing the number of injections prescribed in the current prescription by this time span. This number of doses/week will be used in the cross sectional study as an attribute of the prescription to assess the occurrence of medication errors as described above.

Patients with off-label use:

- Prescribed dulaglutide with no diagnosis of T2DM as defined above, at the beginning of this list of subgroups of populations.
- Prescribed dulaglutide with a diagnosis of T2DM as defined above and without a record of other ADMs during the 6-month baseline period, i.e. dulaglutide was prescribed as first-line therapy.

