
Other comorbidities frequent in T2DM patients: Dyslipidemia Hypertension
 
Macrovascular complications: Ischaemic heart disease
 
Stroke Peripheral arterial obstructive disease
 
Microvascular complications: Diabetic neuropathy Diabetic retinopathy Diabetic nephropathy
	
ICD-10 codes E78 or lipid modifying agents (ATC C10) ICD-10 codes I10-I15 or antihypertensives (ATC C02, C03, C04, C07, C08, C09) with no angina pectoris (I20, I25)
 
ICD-10 codes I20-I25 or antiangina agents (ACT C01D, C07, C08, C09) I61-I64 I70.2
 
G62.9 H36.0 N08.3

Solid tumours (Cancer)
 
 • liver • pancreas • endometrium • colon • rectum • breast • bladder 	
ICD-10 codes C220-C229 ICD-10 codes C250-C259 ICD-10 code C541 ICD-10 codes C182-C189 ICD-10 code C20 ICD-10 codes C500-C509 ICD-10 codes C670-C679

Dulaglutide dose: per 0.5 ml
	
Dose: 0.75 mg / week 1.5 mg / week >1.5 mg / week

Variables, Subgroups and Measurements of Interest

Variable, subgroup or outcome/measurement	Definition and categories*
Concomitant medications for T2DM , at index date of dulaglutide initiation	
 • Molecule: INN/brand name • ATC code or associated medcode for AMD 
A10A Insulins and analogues
 
 ○ A10AB Insulins and analogues for injection, fast-acting ○ A10AC Insulins and analogues for injection, intermediate-acting ○ A10AD Insulins and analogues for injection, intermediate- or long-acting combined with fast-acting ○ A10AE Insulins and analogues for injection, long-acting ○ A10AF Insulins and analogues for inhalation 
A10B Blood glucose lowering drugs, excluding insulins
 
 ○ A10BA Biguanides ○ A10BB Sulfonylureas ○ A10BD Combinations of oral blood glucose lowering drugs ○ A10BF Alpha glucosidase inhibitors ○ A10BG Thiazolidinediones ○ A10BH Dipeptidyl peptidase 4 (DPP-4) inhibitors ○ A10BX Other blood glucose lowering drugs (exenatide, liraglutide, lixisenatide, albiglutide), excluding insulins 
A10P SGLT2 Inhibitors

Other concomitant medications , at index date of dulaglutide initiation	
 • ATC codes or associated medcode for main pharmacological classes.
History of medications for T2DM , during 6-month baseline period	
 • ATC code or associated medcode for anti-diabetes medications (see above)

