History of other medications , during 6-month baseline period	
 • ATC code or associated medcode for main pharmacological classes.
Off-Label Use	
 • Patients without T2DM • Patients with T2DM for whom dulaglutide was prescribed as first-line therapy

Variable, subgroup or outcome/measurement	Definition and categories*
T2DM	Any of the below conditions: 
 • ICD-10 code E11 • ATC codes A10P or A10X • ATC codes A10A initiated at age>30 • ICD-10 codes E14 first recorded at age>30 without ATC code A10A in the previous 6 months

Abbreviations: ALT= alanine amino transferase; AST= aspartate amino transferase; Beta hCG=Beta subunit of human chorionic gonadotrophin; BMI= body mass index; eGFR= estimated glomular filtration rate; HDL-C= high density lipoprotein cholesterol; ICD-10= International classification of disease, 10th version; LDL-C= low density lipoprotein cholesterol; T2DM= type 2 diabetes mellitus; UK= United Kingdom.

* continuous variables will be also presented by means, SD, et cetera.

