9.4.3. NPR and SPDR in Sweden

Swedish data combine data from the NPR, covering all specialist and hospital care in Sweden, and the SPDR, covering all drugs dispensed at pharmacies in Sweden. The national registers are

updated at least quarterly. These longitudinal data enable to find out comorbidities and historical clinical information on the subjects treated for their T2DM in a hospital, as well as drug prescription details (both primary and secondary care). Prescriptions are not formally linked to an ICD-10 code, but clinical input could provide rationale for linking prescriptions and diagnosis made in secondary care. However, information on patient anthropometric data (height, weight, BMI) are not available through the databases, nor are lab results and clinical measurements such as HbA1c, blood pressure and blood lipid levels.

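### The Section 9.3 T2DM rule lets the dulaglutide prescription itself prove T2DM, so the off-label row for patients without T2DM is 0% by construction, and Table 9.3.2-1 gives a conflicting rule

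*Protocol*

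**What the plan says.** Section 9.3 of the protocol defines T2DM by alternatives joined with *or*: a T2DM diagnosis code, a treatment code, insulin started after age 30, or unspecified diabetes after age 30 without earlier insulin. The treatment alternative is "or with any recorded treatment code for an ADM other than insulin". It has no time window and no exception for the study drug. The first off-label component in the same section refers back to this definition: "Prescribed dulaglutide with no diagnosis of T2DM as defined above, at the beginning of this list of subgroups of populations". The second component is T2DM with no other ADM recorded in the 6-month baseline, that is, first-line use.

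The PASS Information table gives the active substance as "Dulaglutide (ATC code: A10BX". Section 9.2.2 admits "Patients for whom a treatment with dulaglutide is initiated during the observation period".

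The T2DM row of Table 9.3.2-1 replaces the treatment alternative with "ATC codes A10P or A10X". The concomitant-medication row of the same table uses a different code for the non-insulin drugs, "A10B Blood glucose lowering drugs, excluding insulins". Under it come biguanides, sulfonylureas, oral combinations, alpha-glucosidase inhibitors, thiazolidinediones, DPP-4 inhibitors and A10BX. There A10P means SGLT2 inhibitors only, and A10X does not appear.

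**The concern.** Two definitions of the same concept stand in one document, and neither does its job as written.

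The Section 9.3 rule is circular: the prescription whose indication is being judged also serves as the evidence for the indication. The row of mock Table 9.7.4-1 for patients without T2DM would be empty and would look like a reassuring result.

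The Table 9.3.2-1 rule can err the other way. Section 9.9.1 says treatment codes are there to make up for under-recorded diagnoses, but a rule without A10B cannot do this for users of the main oral classes. Sweden is the most exposed, because its diagnosis register is described as "covering all specialist and hospital care in Sweden", so T2DM managed in primary care may carry no diagnosis code.

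The only sensitivity analysis planned for off-label use (Section 9.7.3) varies the age limits in the insulin and unspecified-diabetes criteria. It cannot move the zero and does not touch the missing A10B classes.

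**Working it through.** **The plan's own figures.** The protocol states no expected off-label proportion. Its only calculation is study size (Section 9.5.1), n = p(1−p)z²/e² with p = 0.5 and z = 1.96. This gives 384.1 for ±5%, 1067.1 for ±3% and 96.04 (97 rounded up) for ±10%, against the stated 384, 1066 and 97. They agree apart from a difference of about one patient at ±3%, which does not matter here. What matters is the resulting minimum of 100 patients in the smallest country, together with the rule in Section 9.7.1 that countries and years are not pooled.

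**Section 9.3 rule.**
1. Every included patient has a dulaglutide record (Section 9.2.2).
2. Dulaglutide is coded A10BX, a non-insulin ADM (PASS Information table).
3. Any non-insulin ADM record meets the T2DM definition (Section 9.3).
4. So the number without T2DM is 0 of N for any data. The exact two-sided 95% upper limit for 0 of 100 is 1 − 0.025^(1/100) = 3.6%.

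**Each rule applied to typical records.** The last column uses a treatment criterion of any non-insulin ADM other than dulaglutide. ADMs named in a profile are taken as recorded in the baseline period.

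| Patient record before dulaglutide | Section 9.3 as written | Table 9.3.2-1 read literally | Table if A10X means A10BX | Dulaglutide excluded, A10B included |
|---|---|---|---|---|
| No diabetes record, no other ADM | T2DM, first-line | Without T2DM | T2DM, first-line | Without T2DM |
| Type 1, only insulin, started at or before 30 | Not off-label | Without T2DM | Not off-label | Without T2DM |
| Metformin or sulfonylurea; no E11, no qualifying E14, no insulin started after 30 | Not off-label | Without T2DM | Not off-label | Not off-label |
| E11 and metformin | Not off-label | Not off-label | Not off-label | Not off-label |
| E11, no other ADM | T2DM, first-line | T2DM, first-line | T2DM, first-line | T2DM, first-line |

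Under Section 9.3 the first patient stays in total off-label use but in the wrong row. The second leaves off-label use altogether.

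**Size of the error under the table read literally.** Let t be the true share without T2DM. Let u be the share of T2DM initiators whose only T2DM evidence is an A10B drug other than dulaglutide: no E11, no qualifying E14, no insulin started after 30, no A10P or A10X record. Then

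reported share = t + (1 − t)u.

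The documents give neither t nor u, so both are assumptions. For t = 2%:
- u = 2%: 0.02 + 0.98 × 0.02 = 4.0%
- u = 5%: 0.02 + 0.98 × 0.05 = 6.9%
- u = 10%: 0.02 + 0.98 × 0.10 = 11.8%
- u = 20%: 0.02 + 0.98 × 0.20 = 21.6%

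Over the same u, t = 1% gives 3.0% to 20.8% and t = 5% gives 6.9% to 24.0%. In every case Section 9.3 as written reports 0%, and the aligned definition reports t.

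**The case against.** The best defence is that the intent is plain. The first-line rule speaks of *other* ADMs, the A10BX entry among concomitant drugs names four other GLP-1 receptor agonists and not dulaglutide, and the mock table keeps a row for patients without T2DM, which nobody would do expecting it to be empty. A programmer might exclude dulaglutide unprompted. This shows that the repair is small, not that the text is right. The protocol sets the study drug apart where it needs to for first-line use and does not do so in the T2DM rule. Nor can this be left to the SAP: Section 9.7.5 bases the SAP on the protocol, and Section 9.3.2 defers only the CPRD Read codes.

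Four stronger readings are tempting, and the documents do not support them.
- *Reported off-label use would be zero.* Only one row is forced to zero. The first-line component still fills, partly with patients who belong in the other row.
- *The table certainly inflates.* This depends on A10X. If it is a misprint for A10BX, it is dulaglutide's own code; the table is then circular too and also gives 0%.
- *The Swedish error equals the share of patients managed only in primary care.* Such a patient may still qualify through insulin started after 30, an SGLT2 inhibitor, or an earlier specialist or hospital diagnosis. That share is at most an upper bound, and the protocol does not give it.
- *The false zero would carry the precision of 1,000 patients.* That number triggers the start of the study across databases. Results are reported by country and year, and only 100 is set as a minimum for a country.

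**Conclusion.** The point stands as an error in the stated rule. Under Section 9.3 the share of initiators without T2DM is 0% by construction in every country and wave. This follows from the wording alone and needs no assumption. Patients with no diabetes record and no other ADM move to the T2DM first-line row, which Section 9.9.1 already tells readers is an overestimate. Type 1 patients on insulin started at or before age 30 drop out of off-label use. The total is therefore misallocated and partly lost, but not forced to zero.

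Table 9.3.2-1 contradicts the text. Read literally, it overstates the share without T2DM whenever any T2DM initiator has only A10B evidence. The direction is certain on that reading, but the size cannot be estimated from the documents; 4.0% to 21.6% against a true 2% rests wholly on the assumed u of 2% to 20%. If A10X means A10BX, the table repeats the circularity. Either way a primary-objective result depends on which part of the protocol is programmed, so this should be settled before any data are extracted.

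**What to change.** Use one T2DM definition in Section 9.3 and in the T2DM row of Table 9.3.2-1. Its treatment criterion should be a record of a non-insulin ADM other than dulaglutide: A10B except dulaglutide, plus SGLT2 inhibitors under whatever code each database uses. This replaces the A10P or A10X entry. The diagnosis, insulin and unspecified-diabetes criteria can stay as they are, and so can the age-limit sensitivity analysis.

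A rule that a type 1 code overrides treatment evidence is not needed for this repair. It would be debatable, because Section 9.9.1 warns that diagnoses may be missing or wrongly reported.

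The cost is an edit to two places in the protocol and to the code lists. No new data, patients or analyses are required.

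### The T2DM definition ignores a recorded type 1 code and its insulin look-back can never fail, so some dulaglutide use in type 1 diabetes is counted as on-label

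*Protocol*

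**What the plan says.** Section 9.3 of the protocol lists four alternative criteria for T2DM. The first is a T2DM code on record. The second is worded "or with any recorded treatment code for an ADM other than insulin". The third is insulin begun after age 30, and the fourth is an unspecified diabetes code first seen after that age with no earlier insulin. For the third criterion, the start is "defined as no record of insulin therapy during 6 months prior to first record of insulin treatment".

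Table 9.3.2-1 repeats the logic under "Any of the below conditions". Its insulin line, "ATC codes A10A initiated at age>30", states no look-back.

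Off-label use has two branches in Section 9.3. The first is "Prescribed dulaglutide with no diagnosis of T2DM as defined above". The second is T2DM by that definition with no other anti-diabetes medication (ADM) in the 6-month baseline period. Table 9.3.2-1 lists insulins among the diabetes medications, so insulin in baseline takes a patient out of the second branch.

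Section 9.2.2 requires 6 months of history before the first dulaglutide prescription and applies no exclusions. Type 1 diabetes appears in no criterion, sensitivity analysis or listed limitation.

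**The concern.** The protocol describes dulaglutide as approved for T2DM, so by its own definitions a patient with type 1 diabetes belongs among patients without T2DM. Two features of the definition work against that.

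- **No override.** The criteria are joined by 'or', so one treatment proxy outweighs an explicit type 1 diagnosis.
- **An empty look-back.** The insulin criterion is meant to identify insulin started after age 30. It actually identifies a first insulin record after age 30, even when the patient's data begin that day. For dulaglutide the same section has the missing safeguard: "if no prior history is available to check the above criteria, the prescription is not considered as an initiation".

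Off-label use is a subgroup of the primary objective and the whole of the secondary objective. An error that hides off-label use makes the result look more reassuring than it should.

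**Working it through.** The plan gives no figure on this point that could be reproduced. The check is to run patients through the rules as written.

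**1. The look-back.** Let t be the date of the first insulin record. The test asks for no insulin record in the 6 months before t. By definition of t there is none, so the test is true for everyone. The history required by Section 9.2.2 runs back from the first dulaglutide prescription, not from t, and so does not supply the missing check. The unspecified-diabetes criterion differs: its look-back runs from the first diabetes diagnosis, so it can fail.

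**2. Classification.** Each patient below has a type 1 code, no T2DM code and insulin in baseline, except in the last row. Section 9.3 does not say whether dulaglutide itself counts as a non-insulin ADM, so three readings were used.

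| Patient | Text, dulaglutide counted | Text, dulaglutide left out | Table 9.3.2-1 |
|---|---|---|---|
| First insulin record at 35, already on insulin | on-label | on-label | on-label |
| Observed insulin start at 40 | on-label | on-label | on-label |
| First insulin record at 55, already on insulin | on-label | on-label | on-label |
| First insulin record at 22, no other ADM | on-label | off-label | off-label |
| First insulin record at 22, metformin recorded | on-label | on-label | off-label |
| First insulin record at 22, SGLT2 inhibitor recorded | on-label | on-label | on-label |
| First insulin record at 40, no ADM in baseline | off-label, as first-line | off-label, as first-line | off-label, as first-line |

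The metformin row differs because the table's treatment line names only A10P and A10X, while the same table lists biguanides under A10B.

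**3. Effect of the two remedies.**

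- If a type 1 code without a T2DM code overrides the proxies, all seven patients become off-label without T2DM under every reading.
- If only 6 months of observed insulin-free history is required, the patients first recorded at 35 and 55 are reclassified, and only when dulaglutide is not counted as an ADM. The observed start at 40 stays on-label. The look-back therefore cannot replace the override.

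**4. Section 9.7.3.** The sensitivity analysis uses two age bands, above 30 to below 50, and above 50. In the second band the patients first recorded at 35 and 40 no longer qualify through insulin, but the patient at 55 still does. In the first band this is reversed. Each band also drops genuine T2DM patients who started insulin at the other ages, so the difference between the two results cannot be read as the type 1 effect.

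**5. Truncated records.** SIDIAP dispensing data begin after 2005 (Table 9.4.2-1). Taking 2005 as the start, a patient already on insulin has a first record after age 30 if born before about 2005 − 30 = 1975, that is, older than about 2015 − 1975 = 40 in the 2015 wave. For age 50 the figures are 2005 − 50 = 1955 and 2015 − 1955 = 60. In Disease Analyzer a patient is followed at the same GP (Section 9.4.1), so a change of GP can also create a new first record.

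**6. Size, by assumption only.** Assume that type 1 patients are 0.5% to 5% of initiators and that 50% to 100% of them are affected.

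- Low: 1000 × 0.005 × 0.5 = 2.5 patients, or 0.25 percentage points.
- High: 1000 × 0.05 × 1 = 50 patients, or 5 percentage points.

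In a country with the minimum of 100 initiators, the same range is 0.25 to 5 patients.

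**The case against.** The strongest defence is that the proxies are deliberate. Section 9.9.1 says treatment codes are used because some diagnoses are absent or wrongly reported. In Sweden, diagnoses come from specialist and hospital care (Section 9.4.3). A T2DM patient treated in primary care, on insulin since before the data begin and with no T2DM code or other ADM, is recognised only through the insulin proxy. Making a strict look-back the primary rule would move that patient falsely to off-label. This stands, and it shapes the fix. It does not justify letting a proxy outrank a contrary diagnosis that is recorded.

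Whether a type 1 code should outrank the proxies is also a trade between sensitivity and specificity, since some such codes will be wrong. That stands as a cost. The general statements on misclassification in Section 9.9.1 do not settle the matter: the only direction stated there for off-label use is overestimation of first-line use, and this error runs the other way.

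Three stronger readings are tempting and are not supported:

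- *Most type 1 use is hidden.* The protocol gives neither the share nor the ages of type 1 initiators. Some type 1 patients stay off-label, as the table above shows.
- *The sensitivity analysis is useless.* The band above 50 releases patients first recorded on insulin between 30 and 50, unless another criterion holds them.
- *Swedish drug records start in 2005.* Table 9.5.2-1 gives two years for Sweden without tying either to a register. It gives earlier starts for France (1997), Germany (1992) and the UK (1994), and the three countries are still to be chosen.

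**Conclusion.** The point holds for a defined group: insulin-treated patients with a type 1 code, no T2DM code, an ADM in baseline, and either a first database insulin record after age 30 or a qualifying non-insulin ADM. As written, they are counted as on-label, and the number of patients without T2DM is too low by that amount. Type 1 patients with no ADM in baseline who meet a T2DM proxy remain off-label but are labelled as first-line T2DM use.

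The mechanism follows from the wording alone. The size does not: 0.25 to 5 percentage points rests entirely on the assumed shares. The net error in total off-label use is also unknown, because the acknowledged overestimate of first-line use acts in the opposite direction. The definition and its codes are fixed in the protocol itself, so the correction belongs there.

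**What to change.** 1. In Section 9.3 and Table 9.3.2-1, let a recorded type 1 code (E10 or the Read equivalent) without a T2DM code override the treatment proxies and place the patient among those without T2DM.
2. Show patients with both type 1 and type 2 codes in a separate row. Split the patients without T2DM into those with a type 1 code and those with no evidence of diabetes.
3. Replace the empty look-back with at least 6 months of observed insulin-free drug history before the first insulin record. Either apply it as a sensitivity analysis, or show patients who lack both that history and any diagnosis code as diabetes type undetermined, not as off-label. State that dulaglutide itself does not count under the non-insulin criterion; otherwise this step changes nothing.

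The cost is wording, one code list and a few table rows before extraction. Table 9.4.5-1 lists diagnosis codes as available in all five sources. There are two downsides. T2DM patients miscoded only as type 1 will move to off-label, which the split rows make visible. A strict look-back would lose insulin-treated T2DM patients whose diagnosis is not recorded, which is why it should not be the primary rule without the undetermined category.
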